5.7 Diet and Other Considerations

5.7.1 Diet

Subjects should maintain a normal diet unless modifications are required to manage an AE such as diarrhea, nausea, or vomiting.

5.7.2 Contraception

Pembrolizumab may have adverse effects on a fetus in utero. Furthermore, it is not known if pembrolizumab has transient adverse effects on the composition of sperm. Non-pregnant, non-breast-feeding women may be enrolled if they are willing to use adequate birth control or are considered highly unlikely to conceive. Highly unlikely to conceive is defined as 1) surgically sterilized, or 2) postmenopausal (a woman who is ≥ 45 years of age and has not had menses for greater than 1 year will be considered postmenopausal), or 3) not heterosexually active for the duration of the study. Birth control methods can be barrier methods or hormonal method to prevent pregnancy. Subjects should start using birth control from study Visit 1 throughout the study period up to 120 days after the last dose of study therapy.

The following are considered adequate barrier methods of contraception: diaphragm, condom (by the partner), copper intrauterine device, sponge, or spermicide. Appropriate hormonal contraceptives will include any registered and marketed contraceptive agent that contains an estrogen and/or a progestational agent (including oral, subcutaneous, intrauterine, or intramuscular agents).

Subjects should be informed that taking the study medication may involve unknown risks to the fetus (unborn baby) if pregnancy were to occur during the study. In order to participate in the study they must adhere to the contraception requirement (described above) for the duration of the study and during the follow-up period defined above. If there is any question that a subject will not reliably comply with the requirements for contraception, that subject should not be entered into the study.

5.7.3 Use in Pregnancy

If a subject inadvertently becomes pregnant while on treatment with pembrolizumab, the subject will immediately be removed from the study. The site will contact the subject at least monthly and document the subject's status until the pregnancy has been completed or terminated. The outcome of the pregnancy will be reported to the Hoosier Cancer Research Network (HCRN) **within 1 business day** of becoming aware of the event. HCRN will then report to Merck **within 1 business day** if the outcome is a serious adverse experience (e.g., death, abortion, congenital anomaly, or other disabling or life-threatening complication to the mother or newborn).

The study investigator will make every effort to obtain permission to follow the outcome of the pregnancy and report the condition of the fetus or newborn to HCRN. If a male subject impregnates his female partner the study personnel at the site must be informed immediately and the pregnancy reported to HCRN and to Merck and followed as described above.

5.7.4 Use in Nursing Women

It is unknown whether pembrolizumab is excreted in human milk. Since many drugs are excreted in human milk, and because of the potential for serious adverse reactions in the nursing infant, subjects who are breast-feeding are not eligible for enrollment.

6. TOXICITIES AND DOSE DELAYS/DOSE MODIFICATIONS

The NCI Common Terminology Criteria for Adverse Events (CTCAE) v4 will be used to grade adverse events.

Subjects enrolled in this study will be evaluated clinically and with standard laboratory tests before and at regular intervals during their participation in this study as specified in Study Calendar & Evaluations.

Subjects will be evaluated for adverse events (all grades), serious adverse events, and adverse events requiring study drug interruption or discontinuation as specified in Study Calendar & Evaluations.

6.1 Dose Delay of Pembrolizumab

Adverse events (both non-serious and serious) associated with pembrolizumab exposure may represent an immunologic etiology. These adverse events may occur shortly after the first dose or several months after the last dose of treatment. Pembrolizumab must be withheld for drug-related toxicities and severe or life-threatening AEs as per Table 3.

Table 3: Dose Modification and Toxicity Guidelines of pembrolizumab for Immune-related AEs Associated with Pembrolizumab

General instructions:				

 1. Corticosteroid taper should be initiated upon AE improving to Grade 1 or less and continue to taper over at least 4 weeks. 2. For situations where pembrolizumab has been withheld, pembrolizumab can be resumed after AE has been reduced to Grade 1 or 0 and corticosteroid has been tapered. Pembrolizumab should be permanently discontinued if AE does not resolve within 12 weeks of last dose or corticosteroids cannot be reduced to ≤ 10 mg prednisone or equivalent per day within 12 weeks. 3. For severe and life-threatening irAEs, IV corticosteroid should be initiated first followed by oral steroid. Other immunosuppressive treatment should be initiated if irAEs cannot be controlled by corticosteroids. 				
Immune-related AEs	Toxicity grade or conditions (CTCAEv4.0)	Action taken to pembrolizumab	irAE management with corticosteroid and/or other therapies	Monitor and follow-up
Pneumonitis	Grade 2	Withhold	
 • Administer corticosteroids (initial dose of 1-2 mg/kg prednisone or equivalent) followed by taper 	
 • Monitor participants for signs and symptoms of pneumonitis • Evaluate participants with suspected pneumonitis with radiographic imaging and initiate corticosteroid treatment • Add prophylactic antibiotics for opportunistic infections
	Grade 3 or 4, or recurrent Grade 2	Permanently discontinue		
Diarrhea / Colitis	Grade 2 or 3	Withhold	
 • Administer corticosteroids (initial dose of 1-2 mg/kg prednisone or equivalent) followed by taper 	
 • Monitor participants for signs and symptoms of enterocolitis (ie, diarrhea, abdominal pain, blood or mucus in stool with or without fever) and of bowel perforation (ie, peritoneal signs and ileus). • Participants with \geq Grade 2 diarrhea suspecting colitis should consider GI consultation and performing endoscopy to rule out colitis. • Participants with diarrhea/colitis should be advised to drink liberal quantities of clear fluids. If sufficient oral fluid intake is not feasible, fluid and electrolytes should be substituted via IV infusion.
	Grade 4	Permanently discontinue		

Immune-related AEs	Toxicity grade or conditions (CTCAEv4.0)	Action taken to pembrolizumab	irAE management with corticosteroid and/or other therapies	Monitor and follow-up
AST / ALT elevation or Increased bilirubin	Grade 2	Withhold	
 Administer corticosteroids (initial dose of 0.5- 1 mg/kg prednisone or equivalent) followed by taper 	
 Monitor with liver function tests (consider weekly or more frequently until liver enzyme value returned to baseline or is stable)
	Grade 3 or 4	Permanently discontinue	
 Administer corticosteroids (initial dose of 1-2 mg/kg prednisone or equivalent) followed by taper 	
Type 1 diabetes mellitus (T1DM) or Hyperglycemia	Newly onset T1DM or Grade 3 or 4 hyperglycemia associated with evidence of β -cell failure	Withhold	
 Initiate insulin replacement therapy for participants with T1DM Administer anti-hyperglycemic in participants with hyperglycemia 	
 Monitor participants for hyperglycemia or other signs and symptoms of diabetes.
Hypophysitis	Grade 2	Withhold	
 Administer corticosteroids and initiate hormonal replacements as clinically indicated. 	
 Monitor for signs and symptoms of hypophysitis (including hypopituitarism and adrenal insufficiency)
	Grade 3 or 4	Withhold or permanently discontinue ¹		
Hyperthyroidism	Grade 2	Continue	
 Treat with non-selective beta-blockers (eg, propranolol) or thionamides as appropriate 	
 Monitor for signs and symptoms of thyroid disorders.
	Grade 3 or 4	Withhold or permanently discontinue ¹		
Hypothyroidism	Grade 2-4	Continue	
 Initiate thyroid replacement hormones (eg, levothyroxine or liothyronine) per standard of care 	
 Monitor for signs and symptoms of thyroid disorders.
Nephritis and Renal dysfunction	Grade 2	Withhold	
 Administer corticosteroids (prednisone 1-2 mg/kg or equivalent) followed by taper. 	
 Monitor changes of renal function
	Grade 3 or 4	Permanently discontinue		

Immune-related AEs	Toxicity grade or conditions (CTCAEv4.0)	Action taken to pembrolizumab	irAE management with corticosteroid and/or other therapies	Monitor and follow-up
Myocarditis	Grade 1 or 2	Withhold	
 Based on severity of AE administer corticosteroids 	
 Ensure adequate evaluation to confirm etiology and/or exclude other causes
	Grade 3 or 4	Permanently discontinue		
All other immune-related AEs	Intolerable/persistent Grade 2	Withhold	
 Based on type and severity of AE administer corticosteroids 	
 Ensure adequate evaluation to confirm etiology and/or exclude other causes
	Grade 3	Withhold or discontinue based on the type of event. Events that require discontinuation include and not limited to: Gullain-Barre Syndrome, encephalitis		
	Grade 4 or recurrent Grade 3	Permanently discontinue		

1. Withhold or permanently discontinue pembrolizumab is at the discretion of the investigator or treating physician.
 
NOTE: For participants with Grade 3 or 4 immune-related endocrinopathy where withhold of pembrolizumab is required, pembrolizumab may be resumed when AE resolves to \leq Grade 2 and is controlled with hormonal replacement therapy or achieved metabolic control (in case of T1DM).
				

6.2 Dose Modification of Sylatron

Table 4: Dose Modification Guidelines of Sylatron for Drug-Related Adverse Events

Resume treatment at reduced dose (see Table 5)	Withhold treatment	Permanently discontinue treatment
Absolute Neutrophil Count (ANC) $\geq 0.5 \times 10^9/L$	Absolute Neutrophil Count (ANC) $< 0.5 \times 10^9/L$	Persistent or worsening severe neuropsychiatric disorders toxicity
Platelet Count (PLT) $\geq 50 \times 10^9/L$	Platelet Count (PLT) $< 50 \times 10^9/L$	New or worsening retinopathy
Non-hematologic toxicity has completely resolved or improved to Grade 1	Non-hematologic toxicity Grade ≥ 3	Grade 4 non-hematologic toxicity
ECOG PS 0-1	ECOG PS ≥ 2	Inability to tolerate a dose of 60mcg/week

Table 5: Sylatron Dose Modifications

Dose level -1	120 mcg weekly
Dose level -2	60 mcg weekly

6.3 Subject Withdrawal/Protocol Therapy Discontinuation

Subjects may withdraw consent at any time for any reason or be dropped from the trial at the discretion of the site investigator should any untoward effect occur. In addition, a subject may be withdrawn by the site investigator or the sponsor-investigator if enrollment into the trial is inappropriate, the trial plan is violated, or for administrative and/or other safety reasons.

A subject must be discontinued from the trial for any of the following reasons:

- The subject or legal representative (such as a parent or legal guardian) withdraws consent.
- Confirmed radiographic disease progression
NOTE: A subject may be granted an exception to continue on treatment with confirmed radiographic progression if there is objective clinical benefit, please see Section 5.3
- Unacceptable adverse experienced
- Intercurrent illness that prevents further administration of treatment
- Site investigator's decision to withdraw the subject
- The subject has a confirmed positive serum pregnancy test
- Noncompliance with trial treatment or procedure requirements
- The subject is lost to follow-up
- Protocol therapy interrupted for > 12 weeks
- Completed 24 months of uninterrupted treatment with pembrolizumab or 35 administrations of pembrolizumab, whichever is later. **NOTE:** 24 months of pembrolizumab is calculated from the date of first dose.
- Administrative reasons

The End of Treatment and Follow-up visit procedures are listed in Section 7. After the end of treatment, each subject will have follow up visit (1) at 30 days after last dose of study treatment. Serious adverse events will be collected for 90 days after last dose of study treatment (follow up visit 2). Follow up for patients that have not experienced progression will occur every 9 weeks \pm 7 days. This may be done by phone call or other avenues as appropriate. Every effort should be made to obtain information on radiology scans or other types of disease assessment documentation. Once a subject experiences confirmed disease progression or starts a new anti-cancer therapy, the subject moves into the survival follow-up phase and should be contacted by telephone every 12 weeks \pm 7 days to assess for survival status until death, withdrawal of consent, or the end of the study, whichever occurs first.

6.4 Subject Replacement Strategy

If all four sites have more eligible patients than the available slots, the order of enrollment will rotate among the four sites. Otherwise the patients will be enrolled according to the order they become eligible for enrollment.

6.5 Clinical Criteria for Early Trial Termination

Early trial termination will be the result of the criteria specified below:

1. Quality or quantity of data recording is inaccurate or incomplete
2. Poor adherence to protocol and regulatory requirements
3. Incidence or severity of adverse drug reaction in this or other studies indicates a potential health hazard to subjects
4. Plans to modify or discontinue the development of the study drug. In the event of Merck decision to no longer supply study drug, ample notification will be provided so that appropriate adjustments to subject treatment can be made.

7. STUDY CALENDAR & EVALUATIONS

Study Evaluation Cycle = 21 days	Screening	On Treatment Cycle 1-n	End of Treatment Visit ¹¹	Safety Follow Up Visit ¹²	Long Term Follow Up ¹³
	≤ 28 days	Day 1 ± 5 days	± 7 days	30 days after EOT/study drug ± 7 days	Every 12 weeks after Visit 2
REQUIRED ASSESSMENTS					
Informed Consent	X				
Medical History ¹	X				
Diagnosis and Staging ¹	X				
Physical Exam ²	X	X ¹⁰	X	X	
Vital signs and ECOG Performance Status ³	X	X	X	X	
Baseline ophthalmologic assessment ⁴	X				
AEs & concomitant medications	X	X	X	X	
LABORATORY ASSESSMENTS					
Complete Blood Cell Count with diff (CBC)	X	X ¹⁰	X	X	
Comprehensive Metabolic Profile (CMP) and amylase	X	X ¹⁰	X	X	
PT/INR and aPTT	X	X ¹⁰	X	X	
Thyroid Function (TSH, free T4, T3)	X	X ¹⁰	X	X	
Urinalysis	X	X ¹⁰	X	X	
Pregnancy test (serum or urine) (WOCBP) ⁵	X				
DISEASE ASSESSMENT					
CT of chest ⁶	X	X			X
CT or MRI of abdomen and pelvis ⁶	X	X			X
MRI Brain ⁶	X	X			X
TREATMENT EXPOSURE					
Sylatron ⁷		X			
Pembrolizumab ⁷		X			
SPECIMEN COLLECTION					
Archival and Newly Obtained Tumor Tissue ⁸	X	X ⁸			
Blood Samples ⁹	X	X	X ⁹	X ⁹	
FOLLOW-UP					
Survival Status, Subsequent Therapy					X

Key to Footnotes

¹ During the medical history other information to be collected includes smoking history, alcohol history, diagnosis and staging and how the healthcare provider and/or subject learned about this study. Diagnosis and staging to include: reviewing pathology report and screening scans. Special attention should be given to the assessment of past or current depression or suicidal tendencies. In addition, if a subject has substance abuse issues, they are at higher risk of relapse. If concerns are identified during this visit, the appropriate referral to psychiatric services should be made to further assess. See SPM for additional information.

² Patients will be screened for depression, suicidal tendencies and possible relapse of substance abuse at each physical exam. If a concern is noted, the patient will be referred for the appropriate mental health evaluation. In addition, cardiac issues will be assessed per SOC and if concerns are identified, appropriate testing should be completed to fully assess the subject. This may include an EKG, ECHO/MUGA or cardiology referral.

³ Vital signs to include blood pressure, weight, and height (screening only) and ECOG performance status

⁴ A baseline ophthalmologic assessment will be done in subjects with pre-existing retinopathy, or history of retinal vein or artery thrombosis.

⁵ For women of childbearing potential (WOCBP): urine or serum β hCG, within 28 days of registration and only if clinically appropriate. If a urine test is done and it is positive or cannot be confirmed as negative, a serum pregnancy test will be required.

⁶ Radiology Imaging for disease assessment will be performed at the following timepoints: screening, at the end of Cycle 3 (9 weeks of combination therapy) then every 9 weeks (3 Cycles). Tumor imaging will be performed after the last on-study scan only for patients who do NOT have radiographic progression: Radiology Imaging should occur at 30 days, then every 9 weeks thereafter until disease (radiographic) progression. MRI of the brain should only be done if the patient is suspected to have a brain lesion.

⁷ Sylatron will start on C1D1 and continue weekly. During the C1D1 clinic visit, subjects will be trained on how to manage sylatron administration at home. Pembrolizumab will start C2D1 and continue every 3 weeks. Please see Section 5 for details regarding sylatron and pembrolizumab administration. A window of ± 5 days is allowed to accommodate for schedule conflicts. Laboratory testing should be performed on the day of study treatment administration.

⁸ Archival tissue will be identified during screening and is required if available for all subjects. All subjects will have a biopsy performed of a safely accessible tumor before starting treatment (within 42 days of starting treatment on this protocol) and 3 weeks later prior to initiation of pembrolizumab (prior to Cycle 2 Day 1). Subjects for whom newly obtained samples cannot be provided (e.g. inaccessible tumor for biopsy or subject safety concerns) may omit both biopsies provided documentation of reason is clear in the medical record.

⁹ Serial blood samples will be collected to support biomarker research at the following timepoints: Prior to treatment (1) C1D1, (2) C2D1, (3) C5D1 (4) C7D1 and (5) End of Treatment/Safety Follow Up Visit. See CLM for additional details.

¹⁰ If screening (baseline) labs and physical exam were performed within 7 days of Cycle 1 Day 1 of treatment, these do not need to be repeated. All laboratory assessments should be done prior to treatment.

¹¹ An end of treatment (EOT) visit will be performed for the following situations: (1) if patient has progressed and a discussion of scans/next treatment is needed or (2) if a patient has experienced toxicities that necessitates study treatment discontinuation. Special attention should be given to the assessment of current depression, suicidal tendencies or relapse of substance abuse. If concerns are identified during this visit, the appropriate referral to psychiatric services should be made to further assess. There may be certain situations in which this visit will take place locally and discussion regarding next steps would occur via phone call. In this case the research specific blood samples would not be done until the safety follow up visit.

¹² A safety follow up visit will be performed about 4 weeks after the EOT visit or last dose of study drug. Special attention should be given to the assessment of current depression or suicidal tendencies in addition to relapse of substance abuse. If concerns are identified during this visit, the appropriate referral to psychiatric services should be made to further assess. After completion of the EOT visit, subjects should be contacted on a monthly basis until 180 days after their last dose of study drug to assess for issues with mood or behavior. If a concern is identified the patient will be referred to the appropriate mental health resources for evaluation. If research specific blood samples were not done during the EOT visit, they should be drawn during this visit. This visit may take place locally if the patient had an EOT visit at the study facility and study specific blood samples were drawn at that time.

¹³ Long Term Follow up will occur every 12 weeks \pm 7 days. This may be done by phone call or other avenues as appropriate. Every effort should be made to obtain information on radiology scans or other types of disease assessment documentation. Follow up will continue until death, withdrawal of consent, or the end of the study, whichever occurs first.

Hematology	Chemistry	Urinalysis	Other
Hematocrit	Albumin	Blood	Serum β -human chorionic gonadotropin [†]
Hemoglobin	Alkaline phosphatase	Glucose	(β -hCG) [†]
Platelet count	Alanine aminotransferase (ALT)	Protein	PT (INR)
WBC (total and differential)	Aspartate aminotransferase (AST)	Specific gravity	aPTT
Red Blood Cell Count	Total protein	Microscopic exam (If abnormal)	Total triiodothyronine (T3)
Absolute Neutrophil Count	Carbon Dioxide ‡	results are noted	Free thyroxine (T4)
Absolute Lymphocyte Count	(CO₂ or bicarbonate)	Urine pregnancy test †	Thyroid stimulating hormone (TSH)
	Sodium		Blood for correlative studies
	Calcium		
	Chloride		
	Glucose		
	Phosphorus		
	Potassium		
	Blood Urea Nitrogen		
	creatinine		
	Total Bilirubin		
	Direct Bilirubin (If total bilirubin is elevated above the upper limit of normal)		
	amylase		
[†] Perform on women of childbearing potential only. If urine pregnancy results cannot be confirmed as negative, a serum pregnancy test will be required. [‡] If considered standard of care in your region.			

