System	Laboratory Value																												
Hematological																													
Absolute neutrophil count (ANC)	$\geq 1,500 /\mu\text{L}$																												
Platelets	$\geq 100,000 /\mu\text{L}$																												
Hemoglobin	$\geq 9 \text{ g/dL}$ or $\geq 5.6 \text{ mmol/L}$ without transfusion or EPO dependency (within 7 days of assessment)																												
Renal																													
Serum creatinine OR Measured or calculated CrCl (GFR can also be used in place of creatinine or CrCl)	$\leq 1.5 \text{ X}$ upper limit of normal (ULN) OR $\geq 60 \text{ mL/min}$ for subject with creatinine levels $> 1.5 \text{ x}$ institutional ULN																												
Hepatic																													
Serum total bilirubin	$\leq 2.0 \text{ X ULN}$																												
AST (SGOT) and ALT (SGPT)	$\leq 3.0 \text{ X ULN}$ OR $\leq 5 \text{ X ULN}$ for subjects with liver metastases																												
Albumin	$> 2.5 \text{ mg/dL}$																												
Coagulation																													
International Normalized Ratio (INR) or Prothrombin Time (PT)	$\leq 1.5 \text{ X ULN}$ unless subject is receiving anticoagulant therapy as long as PT or PTT is within therapeutic range of intended use of anticoagulants $\leq 1.5 \text{ X ULN}$ unless subject is receiving anticoagulant therapy as long as PT or PTT is within therapeutic range of intended use of anticoagulants																												
Activated Partial Thromboplastin Time (aPTT)																													

10. Female subject of childbearing potential should have a negative urine or serum pregnancy within 72 hours prior to receiving the first dose of study medication. If the urine test is positive or cannot be confirmed as negative, a serum pregnancy test will be required.
11. Female subjects of childbearing potential should be willing to use adequate birth control or be surgically sterile, or abstain from heterosexual activity for the course of the study through 120 days after the last dose of study medication. Subjects of childbearing potential are those who have not been surgically sterilized or have not been free from menses for > 1 year.
12. Male subjects should agree to use an adequate method of contraception starting with the first dose of study therapy through 120 days after the last dose of study therapy.

Exclusion Criteria

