3.1 Inclusion Criteria

Subject must meet all of the following applicable inclusion criteria to participate in this study:

1. Be willing and able to provide written informed consent/assent for the trial.
2. Be ≥ 18 years of age on day of signing informed consent.
3. Patients must have received 1 line of prior systemic therapy for metastatic or resectable disease (i.e. patients may have received adjuvant gemcitabine and then later gemcitabine/cisplatin for recurrent metastatic disease)
4. Histological confirmation of cholangiocarcinoma.
5. Have measurable disease based on RECIST 1.1.
6. Be willing to provide tissue from a newly obtained core or excisional biopsy of a tumor lesion. Newly obtained is defined as a specimen obtained up to 6 weeks (42 days) prior to initiation of treatment on Day 1. Subjects for whom newly obtained samples cannot be provided (e.g. inaccessible or subject safety concern) may submit an archived specimen only upon agreement from the sponsor-investigator.
7. Have a performance status of 0 or 1 on the ECOG Performance Scale.

8. Demonstrate adequate organ function as defined in Table 1. All screening labs will be performed within 28 days of registration.

Table 1: Adequate Organ Function Laboratory Values

System	Laboratory Value
Hematological	
Absolute neutrophil count (ANC)	$\geq 1,500 /\mu\text{L}$
Platelets	$\geq 100,000 /\mu\text{L}$
Hemoglobin	$\geq 9 \text{ g/dL}$ or $\geq 5.6 \text{ mmol/L}$ without transfusion or EPO dependency (within 7 days of assessment)
Renal	
Serum creatinine OR Measured or calculated ^a creatinine clearance (GFR can also be used in place of creatinine or CrCl)	$\leq 1.5 \text{ X}$ upper limit of normal (ULN) OR $\geq 60 \text{ mL/min}$ for subject with creatinine levels $> 1.5 \text{ x}$ institutional ULN
Hepatic	
Serum total bilirubin	$\leq 2.0 \text{ X}$ ULN
AST (SGOT) and ALT (SGPT)	$\leq 3.0 \text{ X}$ ULN OR $\leq 5 \text{ X}$ ULN for subjects with liver metastases
Albumin	$\geq 2.5 \text{ mg/dL}$
Coagulation	
International Normalized Ratio (INR) or Prothrombin Time (PT)	$\leq 1.5 \text{ X}$ ULN unless subject is receiving anticoagulant therapy as long as PT or PTT is within therapeutic range of intended use of anticoagulants
Activated Partial Thromboplastin Time (aPTT)	$\leq 1.5 \text{ X}$ ULN unless subject is receiving anticoagulant therapy as long as PT or PTT is within therapeutic range of intended use of anticoagulants

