^a Creatinine clearance should be calculated per institutional standard.	

9. Female subject of childbearing potential should have a negative urine or serum pregnancy within 72 hours prior to receiving the first dose of study medication. If the urine test is positive or cannot be confirmed as negative, a serum pregnancy test will be required.
10. Female subjects of childbearing potential should be willing to use adequate birth control or be surgically sterile, or abstain from heterosexual activity for the course of the study through 120 days after the last dose of study medication (Reference Section 5.5.2). Subjects of childbearing potential are those who have not been surgically sterilized or have not been free from menses for > 1 year.
11. Male subjects should agree to use an adequate method of contraception starting with the first dose of study therapy through 120 days after the last dose of study therapy.

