4. SUBJECT REGISTRATION

All subjects must be registered through HCRN's electronic data capture (EDC) system. A subject is considered registered when an "On Study" date is entered into the EDC system. Subjects must be registered prior to starting protocol therapy.

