10.1.6 Use in Pregnancy and Nursing Women

Based on its mechanism of action, pembrolizumab can cause fetal harm when administered to a pregnant woman. Subjects who are pregnant or planning to become pregnant are not eligible for enrollment. It is unknown whether pembrolizumab is excreted in human milk. Since many drugs are excreted in human milk, and because of the potential for serious adverse reactions in the nursing infant, subjects who are breast-feeding are not eligible for enrollment.

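### The study calendar allows a pregnancy test up to 28 days before registration, at the site's discretion, while eligibility requires a negative test within 72 hours before first dose

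*Combined protocol and SAP*

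**What the plan says.** Section 3.1, inclusion criterion 9, asks women of childbearing potential for a "negative urine or serum pregnancy within 72 hours prior to receiving the first dose of study medication". Item 10 of the synopsis inclusion list gives the same rule. The criterion's own verb is the softer one (should), but section 3.1 opens with "Subject must meet all of the following applicable inclusion criteria to participate in this study", so the test is a condition of entry.

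The study calendar in section 7 has one row for the test. It is marked in the screening column only, which is headed as 28 days or less. Footnote 5, attached to that row and already restricted to women of childbearing potential, places the test "within 28 days of registration and only if clinically appropriate". The note under the laboratory table that follows the calendar footnotes says "Perform on women of childbearing potential only"; it gives no timing and no discretion to omit the test.

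Section 4 links registration to dosing only by order: "Subjects must be registered prior to starting protocol therapy". It sets no maximum interval between the two.

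**The concern.** One safety test has two rules in current protocol text. Calendars are what sites commonly schedule from, and this one gives no prompt to time the test close to the first dose. A site that follows it could enrol a woman who does not meet criterion 9, or give the first dose on a test more than 72 hours old. If the site uses the discretionary phrase and overlooks criterion 9, there would be no test at all.

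The discretion is the more serious difference. Because footnote 5 already applies only to women of childbearing potential, its closing condition cannot merely exclude women who are unable to conceive. Read naturally, it lets a site skip a test that criterion 9 makes mandatory.

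What is at stake is fetal exposure and avoidable eligibility deviations. Section 10.1.6 states that "pembrolizumab can cause fetal harm when administered to a pregnant woman", and section 10.2.6 reserves Sylatron in pregnancy for cases where benefit justifies the fetal risk. The calendar schedules no later pregnancy test, so no planned repeat would catch an out-of-date or omitted screening test. Sample size, error rates and the primary analysis are not affected.

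**Working it through.** The plan has no figure to reproduce here. The check sets the two rules side by side, looks for any other text that reconciles them, and then sizes the gap.

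**1. The two rules**

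| | Criterion 9 / synopsis item 10 | Calendar footnote 5 |
|---|---|---|
| Anchor | First dose | Registration |
| Window | 72 hours | 28 days |
| Obligation | Every woman of childbearing potential | Only where judged clinically appropriate |

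**2. Does anything else in section 7 restore the 72-hour test?**

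- *The calendar row* is marked at screening only, with nothing on Day 1 of any cycle.
- *Footnote 7* says laboratory tests are done on the day of treatment. It is attached to the drug rows, and the pregnancy test has no on-treatment mark, so the sentence does not clearly reach it.
- *Footnote 10* waives repeat testing when screening work falls within 7 days of Cycle 1 Day 1. It is not attached to this row, and 7 days (168 hours) would still exceed 72 hours.
- *The laboratory table note* limits the population and is silent on timing. It contrasts with footnote 5 on the discretion to omit the test, but settles nothing about the window.

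None of these supplies the missing instruction. Inclusion criterion 8, which sets screening laboratory work within 28 days of registration, reinforces the calendar's timing.

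**3. Size of the gap**

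Inputs: 28 days (footnote 5), 72 hours (criterion 9), and the interval from registration to first dose, which the documents do not give. I assume 0 to 7 days for that interval.

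Age of test at first dose = 28 days + interval.

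- Interval 0 days: 28 × 24 = 672 hours; 672 / 72 = 9.3 times the limit; 28 − 3 = 25 days outside it.
- Interval 7 days: (28 + 7) × 24 = 840 hours; 840 / 72 = 11.7 times the limit; 35 − 3 = 32 days outside it.

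The upper figure illustrates the assumption. It is not a bound, since section 4 sets no maximum.

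**4. What the 72-hour rule itself covers**

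The first dose of study medication is Sylatron on Cycle 1 Day 1; pembrolizumab starts on Cycle 2 Day 1, nominally 21 days later (section 5.2). A test taken 0 to 3 days before Cycle 1 Day 1 is therefore 21 to 24 days old at the first pembrolizumab dose. Aligning the calendar with criterion 9 protects the first Sylatron dose, as criterion 9 does, and goes no further.

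**The case against.** The best answer is that the controlling rule is already stated twice and is mandatory. A calendar footnote cannot waive an inclusion criterion, and an untested woman of childbearing potential stays ineligible whatever footnote 5 says. The two texts can also be read as cumulative: footnote 5 repeats the general 28-day screening window and criterion 9 adds a tighter condition before dosing. One test within 72 hours of first dose can satisfy both. Exclusion 16 and the contraception rules (inclusion criterion 10 and section 5.7.2) lower the risk further, and the number of women of childbearing potential among the 44 to 46 planned patients is not given and may be small.

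Much of this stands. A breach is possible, not certain, and a site that applies the eligibility list will comply. An omitted test happens only if a site relies on the footnote and overlooks criterion 9. The ratios in the working compare windows with different anchors and depend on an assumed interval; the firm statement is 28 days at registration against 72 hours at first dose.

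The cumulative reading does not rescue the discretionary phrase, however. It can explain two windows, but not why a test required of every woman of childbearing potential should also be optional for them. That the eligibility list governs is a reason to correct the calendar.

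**Conclusion.** The concern holds. The calendar and the eligibility criteria conflict on when the pregnancy test is done and on whether it must be done at all, and no other calendar text resolves this. Followed as written, footnote 5 permits a test 28 days old at registration where the limit is 72 hours at first dose. On an assumed 0 to 7 days to dosing, that is 28 to 35 days old at first dose. The textual conflict is certain. Whether a breach follows depends on sites scheduling from the calendar without applying criterion 9. This should be corrected as a safety and eligibility matter.

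**What to change.** Reword footnote 5 to require a negative urine or serum test within 72 hours before Cycle 1 Day 1 for all women of childbearing potential, and delete its discretionary phrase. Keep the existing rule that a positive or unconfirmed urine result leads to a serum test. Add a Cycle 1 Day 1 mark to the pregnancy-test row, to apply when the screening test is older than 72 hours.

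The cost is protocol wording plus at most one repeat urine or serum test per woman of childbearing potential, which criterion 9 already demands.
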